## **Material and Methods**

Present design represents a randomized double-blind clinical trial. Study was approved on June 18, 2019 by Eastern Metropolitan Health Service of Santiago (SSMO) ethics committee. Study was registered at [www.clinicaltrials.gov](http://www.clinicaltrials.gov). Participants were divided in two groups assessed in both presences of MTrPS in shorter upper trapezius muscle. It was recording the PPT and PI before and after intervention. Both groups received therapeutic ultrasound as baseline treatment. Experimental group received microelectrolysis additionally. A reassessment of PPT and PI was done on day one, three and seven post intervention.

*Subjects.* forty-eight healthy volunteers were recruited (23 men, 25 women, average age 22 years). Participants were students of Science Rehabilitation Faculty (SRF) of Andrés Bello University, Santiago de Chile. Number of participants was selected by convenience. An invitation was extended to students through formal communication channels (mailing), student representatives and social networks, summoning two hundred and seven potential participants. Selection was based on a survey whose first part was structured in relation to general demographic participant's data, including name, age, sex, body mass index (BMI), career year, and personal information contact (e-mail and cell phone number). Second part of survey consisted of closed questions constructed by eligibility criteria. Inclusion criteria considered participants over 18 years old, students of SRF and positive hypersensitive MTrPs. Exclusion criteria include neck or shoulders pathologies in the last 6 months (as fractures, sprains, tendinopathies, dislocations or muscle tears), cervical pain, sensitivity alterations such as hypesthesia, anesthesia or hyperesthesia in neck, shoulders and/or arms, wounds or skin alterations in shoulder as psoriasis, scars or keloids, fear to electrotherapy application and analgesic pharmacological treatment at recruitment time (non-steroidal anti-

inflammatory or steroidal drugs). Elimination criteria considered non-tolerance electrotherapy intervention and non-completion of evaluation protocol (attendance at all scheduled sessions). Demographic data were tabulated in Microsoft excel® 2016 program (Table 1, characterization of study groups).

Variable	MEP (n = 24)	Control (n = 24)	p-value	Sample distribution
sex (%) men women	11 (22,9%) 13 (27,1%)	12 (25,0%) 12 (25,0%)	p = 0,7730*	Normal *
Age (mean, +/- DS)	22,5 +/- 1,9	22,0 +/- 1,6	p = 0,2993**	Normal **
BMI (Kg/m2) (mean +/- DS)	24,5 +/- 3,4	22,9 +/- 2,3	p = 0,0616**	Normal **
Short trapezius muscle laterality (%) right left	17 (70,8%) 7 (29,2%)	20 (83,3%) 4 (16,7%)	p = 0,2470***	Normal ***
SP-AC distance (cm) (mean +/- DS)	9,2 +/- 1,8	8,4 +/- 1,7	p = 0,1241**	Normal **
PPTpre 1 (Kg/cm2) (mean +/- DS)	1,4 +/- 0,2	1,4 +/- 0,2	p = 0,5734**	Normal **
PIpre1 (mm) (mean +/- DS)	32,1 +/- 13,6	31,4 +/- 15,1	p = 0,8729**	Normal **

**Table 1. Characterization of study groups.** Variable sex and short trapezius muscle laterality is represented in frequencies (%). Values for continuous variables are in means with their corresponding standard deviation (DS). Variable sex was analyzed using  $\chi^2$  test\*. For the analysis of continuous variables, the T-Student test was used\*\*. Variable short trapezius laterality was analyzed with the F-Fishertest\*\*\*.

**BMI:** body mass index, **SUTL:** short upper trapezius muscle laterality, **SP-AC distance:** distance spinous process from C7 to acromion, **PPTpre:** pain pressure threshold pre intervention at day one, **PIpre:** pain intensity pre intervention at day one. ***p* > 0,05\*\*\*\***

Secondary variables as short upper trapezius muscle laterality (SUTL) and sex were represented as frequencies, while MTrP location distance (MLD) and age was represented as median and BMI in averages. Primary variables included PPT and PI pre-intervention

(PPTpre and PIpre) were expressed as averages with their corresponding standard deviation (x, SD). Data were analyzed to compare homogeneity of groups with STATAv.13 program.

*Equipment.* GYMNA's COMBI 500 electric stimulator was used for ultrasound application at 1MHz, 1.5Watts/cm^2, 100% duty cycle, 5cm^2 ERA and 15 minutes. SVELTIA's DC equipment was used for MEP application. It was used a dispersing electrode (area 28.26cm^2) and an acupuncture needle (0.3x25millimeters). Circuit was closed by placing dispersing electrode in contralateral arm to trapezius muscle to be treated. Current intensity was 600μA at the needle (current density of 1.71mA/cm^2).

[figure not shown]
*Measurement tools.* BASELINE® pressure algometer was used to measure PPT (1cm^2 surface area). Algometry was applied after shortness upper trapezius assessment by placing algometer at the MTrP exerting a perpendicular pressure until user reported pain. Kilograms of pressure per square centimeter (Kg/cm^2) was registered. PI was evaluated with VAS. VAS was applied after algometry recording pain perceived with algometry test.

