## **ABSTRACT.**

**Background:** Percutaneous electrotherapy is today a therapeutic alternative in musculoskeletal conditions. In that sense, percutaneous microelectrolysis (MEP) stands out as treatment for tendinopathies and musculoskeletal pain, such as myofascial trigger points (MTrPs), although more studies are needed to support it.

**Objective:** Investigate effectiveness of MEP in reducing painful pressure threshold (PPT) and pain intensity (PI) in MTrPs.

**Method:** Controlled randomized clinical trial. Research was performed at Physiotherapy Laboratory of Andrés Bello University. Participants were forty-eight volunteers with MTrPs presence in upper trapezius muscle. Both groups received a baseline ultrasound treatment, adding MEP to experimental group. Intervention consisted of a MEP intervention and tree

reevaluation sessions (at day one, three and seven). Direct current was delivered with acupuncture needle directly to MTrP and PPT and PI was reevaluated before and after application. Main outcomes were PPT and PI differences (PPTdiff and PIdiff) between evaluation sessions.

**Results:** MEP demonstrated positive changes increasing PPT (PPTdiff1-1, p=0,0000, PPTdiff2-1, p=0,0000, PPTdiff3-1, p=0,0000) and decreasing PI (PIdiff1-1, p=0,0001, PIdiff2-1, p=0,0001, PIdiff3-1, p=0,0008) in experimental group, and significant differences in PPT at second reevaluation session compared to control group (PPTdiff2-1, p=0,0032).

**Conclusion:** MEP is a good analgesic treatment for MTrPs compared to therapeutic ultrasound, although neither of two therapies seems to be better than other in long term. Two treatments improvements PPT and PI, so MEP can be considered as an effective alternative treatment for MTrPs pain.

**Keywords:** electrotherapy; electrolysis; pain threshold; myofascial pain syndromes; analog visual scale.

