##### 6. Pain pressure threshold (PPTpre) and pain intensity (PIpre) postintervention evaluation.

Completing intervention, participants returned to evaluation station. Evaluator repeated the same assessment protocol made before ultrasound and MEP application, recording PPT and PI postintervention. Variables PPTdiff1-1 and PIdiff1-1 were created based on differences

between algometry and pain intensity measurements before and after intervention. Participants were cited for a reevaluation on day three and seven obtained variables PPT2, PI2, PPT3 and PI3. This allowed to create PPTdiff2-1, PPT3-1, PI diff2-1 and PI diff3-1 variables, that represented differences obtained between the measurements of days three and seven with those obtained on day one before intervention.

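### The reassessment days in Material and Methods contradict the procedure: the first reading is same-session, the later two fall 2 and 6 or 3 and 7 days after treatment, and nothing supports a long-term conclusion

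*Protocol*

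**What the plan says.** The Protocol describes the timing of the assessments in four places.

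- **Material and Methods, opening paragraph:** "A reassessment of PPT and PI was done on day one, three and seven post intervention". The preceding sentences separately say that PPT and PI were recorded before and after the intervention.
- **Abstract, Method:** three "reevaluation sessions (at day one, three and seven"), with no statement of what the days are counted from. PPT and PI are also said to be measured again before and after application.
- **Material and Methods, Table 1 legend:** the baseline PPT is the "pain pressure threshold pre intervention at day one". Baseline PI is labelled in the same way.
- **Procedure, section 6:** "Completing intervention, participants returned to evaluation station", and the evaluator then repeated the assessment. PPTdiff1-1 and PIdiff1-1 are the differences across that session. Participants were called back on days three and seven, and the later variables are differences "between the measurements of days three and seven with those obtained on day one before intervention".

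The Abstract reports "significant differences in PPT at second reevaluation session compared to control group" (PPTdiff2-1, p=0,0032) and concludes that "neither of two therapies seems to be better than other in long term".

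**The concern.** The Abstract names the PPT and PI differences between evaluation sessions as the main outcomes, so the time of each reading is part of the outcome's definition. Read literally, Material and Methods places the readings one, three and seven days after treatment. Procedure section 6 has no next-day reading at all.

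A reader who relies on Material and Methods could take a change measured within the treatment session as an effect that lasts a day, which is a different clinical claim. The same reader cannot tell whether the contrast reported as significant was seen two or three days after treatment. The closing statement about the long term extends a conclusion beyond the last assessment.

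**Working it through.** There is no planning calculation to reproduce: the number of participants was chosen by convenience, and no figure in the Protocol depends on the visit calendar. The check is to match visits to variables and count days.

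**Step 1. What is day one?** The Table 1 legend places the pre-intervention reading at day one, and Procedure section 6 takes differences against day one before intervention. Day one is therefore the treatment day.

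**Step 2. How many post-treatment readings are there?** Taken together, the before-and-after reading and three further reassessments in Material and Methods would need 1 + 3 = 4 post-treatment readings: same session, +1, +3 and +7 days. Procedure section 6 defines three differences per outcome (1-1, 2-1, 3-1), so 3 × 2 = 6 variables over PPT and PI. None corresponds to a next-day visit. The day-one reassessment must therefore be the same-session reading.

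**Step 3. Elapsed days after treatment under each reading of the text.**

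| Reading | 1-1 | 2-1 | 3-1 |
|---|---|---|---|
| (a) Treatment is day 1 throughout (Table 1 legend, Procedure 6) | 0 | 3 − 1 = 2 | 7 − 1 = 6 |
| (b) Material and Methods taken literally | 1 | 3 | 7 |
| (c) First reading same-session, call-backs counted from treatment | 0 | 3 | 7 |

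Reading (b) is excluded for the 1-1 variables by Procedure section 6. Readings (a) and (c) remain. They agree on the first time point and differ by one day on each of the other two, so four of the six variables carry a one-day ambiguity.

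**Step 4. When does the reported between-arm difference fall?** The Abstract counts three sessions at days one, three and seven, so the second is day three. The label PPTdiff2-1 agrees, since Procedure section 6 lists PPT2 for the first of the two call-backs. Elapsed time: 2 days under (a), 3 days under (c).

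**Step 5. How long is follow-up?** The last reading is at 6 days under (a) and 7 days under (b) or (c). Treatment was given once.

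**The case against.** The strongest reply is that this is one loose phrase. With day one as the treatment day, the Abstract's list of sessions, the Table 1 legend and Procedure section 6 all agree. Only the words that count the days from the intervention, in one summary sentence of Material and Methods, conflict with them. The detailed procedure would normally govern, and both the Abstract and Material and Methods disclose that readings were taken before and after treatment. The last assessment day is also visible in the Abstract, so a reader can see the horizon behind the long-term wording.

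Much of this stands, and it rules out several stronger readings that a reader might infer:

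- *Every time of effect is uncertain.* Procedure section 6 fixes the 1-1 variables as same-session; only the later two readings are ambiguous, each by one day.
- *The second reevaluation session could be day three or day seven.* Both the session count and the variable label give day three.
- *The first reading came minutes after treatment.* That is plausible, but no interval is stated; same-session is as far as the text goes.
- *Different sites would follow different calendars.* The Protocol describes a completed study in one laboratory.
- *The treatment comparison is biased.* The schedule is the same in both arms, so the labelling ambiguity does not by itself bias the contrast, and it changes no p-value.

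What the reply does not remove is that the text contradicts itself on the timing of its main outcomes, that the elapsed time of the call-backs is nowhere stated, and that the long-term statement goes beyond the data under every reading of the calendar.

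**Conclusion.** The point holds as a fault in how the outcomes are dated and in the claim about duration; it is not a fault in the comparison of the arms. The reassessment described as day one after the intervention is a same-session reading. The day-three and day-seven visits are 2 and 6 or 3 and 7 days after treatment. The PPT contrast reported as significant is at day three, hence 2 or 3 days after treatment. Follow-up ends 6 or 7 days after one session, so no statement about the long term can be made in either direction.

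This rests on taking Procedure section 6 as the account of what was done, which is reasonable because it is the most detailed and matches the variables defined. If the visit dates showed a separate next-day visit, Procedure section 6 would be the text to correct, and the 1-1 variables would need a new definition.

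**What to change.** 1. Reconcile the opening paragraph of Material and Methods with the Table 1 legend and Procedure section 6, and state once whether the treatment day is day 0 or day 1.
2. Take the elapsed time of each reading from the recorded visit dates and give it beside each variable, including the PPTdiff2-1 result in the Abstract.
3. Describe PPTdiff1-1 and PIdiff1-1 as immediate (same-session) change.
4. In the Abstract's conclusion, replace the long-term wording with *at the last assessment, about one week after a single session*.

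The cost is wording and a check of visit dates. No new data or analysis is needed. The downside is a weaker claim about duration.

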### *Procedure.*

#### 1. Participants

207 surveys were analyzed obtaining 59 potential participants, dropping out five. 54 participants agreed to participate and gave their written consent. Six participants were excluded due absence of MTrPS, obtaining 48 participants (23 men, 25 women). Principal investigator assigned a number to each participant to perform randomization. Conformation of groups was carried out by simple randomization by dark envelopes. Participants didn't know assigned group and were individually cited in following two weeks to physiotherapy laboratory of SRF to be evaluated.

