**Figure 1. Subject recruitment and flow through the study**

## 2. Groups.

Sample was divided by a simple randomization process performed with a random number table, assigned participants to one of two study groups. Sequence of randomization and participants of each group was only known by principal investigator. Working groups were designated as experimental (MEP group, n = 24) and control group (n = 24). None subjects knew the treatment that would be applied. Each participant was evaluated registering their age, BMI and SUTL. Location of MTrP was determined at shortness trapezius muscle, taking as reference a line between superior acromion's midpoint surface and C7 spinous process (PE-AC distance). Algometry and VAS was subsequently applied obtaining the PPT and PI

pre intervention (PPTpre y PIpre). Variables described were compared between groups to assess the homogeneity of them (Table 1). Data reflect the homogeneity of groups at the beginning of the study.

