### 4. Therapeutic ultrasound application.

Participants of both groups received a therapeutic ultrasound treatment. Experimental group received first ultrasound and subsequently MEP, while control group was treated only with ultrasound. Ultrasound intervention protocol was performed in the same way for both groups. Application was performed in an adjoining room by another physiotherapist who didn't know

groups. Treatment was carried out with participant in sitting position applying ultrasound at sensitive point marked by examiner of evaluation station. Ultrasound therapy was delivery at 1MHz, 1.5 Watts/cm^2, 100% duty cycle (SATP: 1.5Watts/cm^2 and SATA:1.5W/cm^2), ERA 5cm^2 and 15 minutes. Once ultrasound intervention was finished, participants of MEP group were taken to microelectrolysis box, while participants of control group returned to evaluation station.

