##### 5. Microelectrolysis application.

Microelectrolysis was performed by another physiotherapist. Before intervention, puncture area was cleaned with alcohol. Procedure was performed with latex gloves. Acupuncture needle was introduced perpendicular to demarcated point of trapezius with 0.14mA intensity. Dispersing electrode was placed in external surface of contralateral arm once chosen trapezius muscle. Inside tissue intensity was raised to 0.6mA. Each participant was instructed to indicate to physiotherapist appearance of burning, pain or great local pressure in order to pause emission. Emission time was recorded until symptoms appeared, indicating T1 time, pausing emission for 30 seconds. Then a second emission was made until participant referred again discomfort symptoms. Second emission time was recorded as T2, pausing application again for 30 seconds. Third and last emission was delivered for same time obtained for T2 or if discomfort appeared before completing that time.

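### The elimination criteria drop randomised participants for events after allocation, including from outcomes already measured

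*Protocol*

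**What the plan says.** After the inclusion and exclusion criteria, the Subjects paragraph of Material and Methods adds a third, separate list: "Elimination criteria considered non-tolerance electrotherapy intervention and non-completion of evaluation protocol (attendance at all scheduled sessions".

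The order of events is in the Procedure sections. Groups were formed by envelope, and then "Participants didn't know assigned group and were individually cited in following two weeks to physiotherapy laboratory of SRF to be evaluated" (section 1, Participants). Section 2 (Groups) gives the size at allocation: "Working groups were designated as experimental (MEP group, n = 24) and control group (n = 24". Treatment follows: "Experimental group received first ultrasound and subsequently MEP, while control group was treated only with ultrasound" (section 4). In the MEP step, "Each participant was instructed to indicate to physiotherapist appearance of burning, pain or great local pressure in order to pause emission" (section 5).

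The outcomes are defined in section 6. "Variables PPTdiff1-1 and PIdiff1-1 were created based on differences" between the day-1 measurements before and after treatment. The later variables are those "that represented differences obtained between the measurements of days three and seven with those obtained on day one before intervention".

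The only losses in the readable text are five drop-outs and six exclusions for absent trigger points, all before the groups were formed. The flow diagram is captioned "Figure 1. Subject recruitment and flow through the study", but the figure itself is not in the text available for review.

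**The concern.** A criterion met only after allocation is not an eligibility criterion. It selects on something that treatment may have influenced, so the arms that remain need no longer be comparable. Two features make this rule worse than it need be.

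First, it is all-or-nothing. Missing one session removes the participant from every comparison, including those for which the data are complete.

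Second, one trigger need not act equally in the two arms. Only MEP participants go on to needle current, and the outcomes are themselves pain measures, so failure to tolerate treatment could be related to outcome. This is possible but not shown. Discomfort during MEP leads to a planned pause, and fear of electrotherapy was already an exclusion.

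If losses differ by arm and relate to outcome, the PPT and PI differences are biased, even at visits where everyone was measured.

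**Working it through.** **1. Participant flow.** From Procedure, section 1: 59 − 5 = 54 and 54 − 6 = 48. From section 2: 24 + 24 = 48. Sex counts in Table 1: 11 + 12 = 23 men and 13 + 12 = 25 women, again 48. The flow closes with no loss after randomisation in the readable text. These are counts at allocation and baseline; no count is given for day 3 or day 7.

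**2. Timing of the triggers.** Allocation comes first, the laboratory visit in the following two weeks, then ultrasound, then MEP in one arm, then reassessment the same day and on days 3 and 7. Non-tolerance and a missed session can therefore only follow allocation.

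**3. What the rule discards.** Two outcomes at four time points (day 1 before, day 1 after, day 3, day 7) make 2 × 4 = 8 values. Missing only day 7 leaves 2 × 3 = 6. Those six fully determine the day-1 and day-3 differences for both outcomes.

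**4. Possible bias at one visit (assumed inputs).** Assume 24 per arm, no true effect, unit SD and a two-sided t-test at 5%. The k MEP participants lowest on a score with correlation ρ to the outcome are removed. Then

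bias = ρ × a(k),

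where a(k) is the expected mean of the 24 − k highest of 24 standard normal values: 0.156, 0.223 and 0.286 for k = 2, 3, 4. At ρ = 0.5 this gives 0.078, 0.111 and 0.143. Simulation of 100,000 trials per scenario agrees:

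| ρ | k removed (MEP only) | Bias (SD) | Two-sided error |
|---|---|---|---|
| 0 | 2 | 0.00 | 4.9% |
| 0 | 4 | 0.00 | 5.0% |
| 0.2 | 2 | 0.031 | 5.1% |
| 0.2 | 4 | 0.057 | 5.4% |
| 0.5 | 2 | 0.078 | 6.0% |
| 0.5 | 3 | 0.111 | 6.8% |
| 0.5 | 4 | 0.144 | 7.9% |

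With the same k removed from both arms at ρ = 0.5, bias is 0.000 to 0.001 SD and the error 5.5 to 5.8%.

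**5. Rule against all collected values, three visits (assumed inputs).** 40,000 trials, between-visit correlation 0.4 to 0.8, and 2 to 4 MEP participants missing day 7 only, with ρ = 0.5.

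- *Absence tied to the day-1 change.* The rule gives bias of 0.08 to 0.14 SD at day 1 and 0.03 to 0.12 SD at days 3 and 7. Using every collected value (day 7 by regression on days 1 and 3 with arm intercepts) stays within 0.003 SD of zero at all three.
- *Absence tied to the unseen day-7 value.* At day 7 the rule gives 0.08 to 0.14 SD, and all collected values give 0.02 to 0.11 SD. This is better but not cured.

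**6. Could it overturn the day-3 result?** The Abstract reports p=0,0032 for the between-group PPT difference at day 3. Assume a t-test. With 24 and 24, t = 3.11 and d = 3.11 × √(2/24) = 0.90 SD. If k MEP participants had been eliminated, the difference is d = t × √(1/(24 − k) + 1/24), with t taken at 46 − k degrees of freedom. Put them back at mean m relative to control, with SD 1 among themselves:

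- difference = [(24 − k)d + km]/24
- pooled variance = [(23 − k) + (k − 1) + ((24 − k)k/24)(d − m)² + 23]/46

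| k | d (SD) | p if added at control mean (m = 0) | m needed for p = 0.05 |
|---|---|---|---|
| 2 | 0.921 | 0.0056 | −2.07 |
| 3 | 0.933 | 0.0077 | −1.31 |
| 4 | 0.947 | 0.0103 | −0.88 |

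For k = 2 and m = 0: difference = 22 × 0.921/24 = 0.844; variance = (21 + 1 + 1.833 × 0.921² + 23)/46 = 1.012; t = 0.844/(1.006 × 0.2887) = 2.91 on 46 degrees of freedom.

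**The case against.** The strongest reply is that the Protocol never says in so many words that eliminated participants leave the analysis. Elimination could mean withdrawal from further participation, with the data handled in an analysis plan that is not shown. That reading fails for attendance. Day 7 is the last session, so someone who misses it has nothing left to be withdrawn from, and elimination can only concern the data. For non-tolerance the wording is more open, and removal from the analysis is an interpretation there, though the natural one since both triggers share one list.

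Three further points stand:

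- Nothing readable shows that the rule was ever applied, and the flow diagram, where losses would normally appear, is not available. The lack of documented eliminations is therefore not evidence of under-reporting.
- The day-7 illustration assumes absence in the MEP arm only, for which the Protocol gives no reason. The arm-specific argument concerns tolerance, and equal losses give no bias.
- The illustrated effects are modest, and the trial is complete, so rewording alone changes nothing already done.

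These points limit the size of the concern. They do not make the rule sound.

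**Conclusion.** The concern holds. The Protocol states a rule that conditions the comparison on events after allocation and discards valid day-1 and day-3 values. The count of six discarded values out of eight follows directly from the outcome definitions.

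The size of any bias is conditional: zero if no one was eliminated, about zero if losses were equal or unrelated to outcome, and 0.03 to 0.14 SD at day 1 if 2 to 4 MEP participants alone were lost with a correlation of 0.2 to 0.5 to outcome. Loss counts, correlations and direction are assumptions; the documents give none of them.

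The day-3 PPT finding is fairly robust. The lost participants would have to average 2.1 SD (two lost) to 0.9 SD (four lost) below the control mean to bring p to 0.05. This should be corrected, but there is no ground for saying that the reported results are wrong.

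**What to change.** Stop using non-tolerance and missed sessions as grounds for leaving the analysis. Analyse all 48 participants in their assigned arm with every PPT and PI value collected: the day-1 differences from the day-1 values, and days 3 and 7 from everyone who attended. A baseline-adjusted repeated-measures model is one option. Keep the completer analysis as a sensitivity analysis.

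State how many participants were eliminated, by arm, visit and reason, unless Figure 1 already does so. If there were none, say so; the analysis then stands unchanged. Whether treatment is stopped for non-tolerance is a separate matter and is not addressed here.

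The cost is one sentence of wording, one statement of eliminations if Figure 1 lacks it, and one reanalysis of existing data only if someone was eliminated. The price is a missing-at-random assumption for absent visits. Values never collected cannot be recovered, and some day-7 bias remains if absence depends on the unseen value.
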